3.10 Intended Use

VerTouch has not yet been cleared by FDA, and is intended to aid in the localization of an interspinous space, and the placement of a needle at the identified site, for diagnostic and therapeutic spinal punctures, including LPs, neuraxial anesthesia (spinals, epidurals, and combined spinal-epidurals), ESIs, and epidural blood patches. The device includes functionality to guide a marking tool or needle.

All investigational devices will have the following label statement: **CAUTION – Investigational Device. Limited by Federal (or United States) Law to Investigational Use.**

4 Device Accountability

4.1 Device Receipt

IntuiTap Medical will ship devices directly to the clinical sites, to the attention of the Investigator or designee at that site. Device receipt and inventory procedures will be determined by the individual sites' standard operating procedures. At a minimum, a device inventory log will record device serial numbers for reusables and disposables, date of receipt, and disposition. At least two sets of reusable VerTouch components will be provided to each clinical setting within each site.

4.2 Device Storage

Devices will be stored in secured rooms under ambient conditions, which meet VerTouch storage requirements. Reusable monitors will be stored on VerTouch charging stations as described earlier; disposables will be stored in their sterile packaging. Device access will be controlled by the Site Investigator or designee.

4.3 Device Dispensing

For each procedure, disposable units will be dispensed for use by the Site Investigator as per the allocation scheme; paired with one of the reusable monitors available within the clinical setting. Device serial numbers will be recorded on the subject's case report form. Device records will be reconciled at each monitoring

visit. This reconciliation will be logged on the device accountability form, and signed and dated by the designated study team member.

4.4 Device Disposition

At the conclusion of the study, all reusable study components, including monitors, charging stations, power adapters, and PC connectors are to be returned to the Sponsor. Consumable components will be recorded and disposed of in accordance with local medical waste regulations. Device return will be recorded and reconciled with device assignment and accountability records.

4.5 Return or Destruction of Unused Devices

Following a full product reconciliation, all unused devices are to be returned to IntuiTap Medical at the address listed below.

IntuiTap Medical, Inc.
[name]
[name]

5 Study Objectives

The primary objective of this study is to establish the superiority of VerTouch versus the conventional palpation technique for the number of needle insertion attempts required in diagnostic and therapeutic neuraxial procedures.

6 Study Design

6.1 Overview of Study Design

After Informed Consent is obtained, subjects will be randomized 1:1 into two groups via the block randomization method with a list held in each test setting. Standard landmarking techniques will be used in both groups to identify the procedure area. For subjects randomized to the tactile-imaging group (T), VerTouch will be used to identify an interspinous space and to place a marker, introducer, or needle. For subjects randomized to the palpation group (P), the palpation-landmarking method will be used. After marker, introducer, or needle placement, the procedure will continue in the usual manner for subjects in both groups (**Figure 6**).

A designated study observer within each setting will record the time to identify an insertion site; time to place the marker, introducer, or needle; number of insertions, re-directions, and bone contacts (counted until confirmation of spinal canal access

can be assessed); incidence of procedure success; subject's level of discomfort during landmarking; and provider's level of confidence with the identified insertion site. Total procedure time, incidence of traumatic taps, and incidence of referrals to radiology or pain management will be recorded in all settings. In anesthesiology, incidences of paresthesia, unintended dural puncture, and conversion from spinal to epidural anesthesia, will be collected for exploratory analysis, where applicable. Any usability issues or device malfunctions observed during the clinical study will also be documented.

[figure not shown]

Figure 5. Overall Study Design

Although spinal punctures in all clinical settings involve the same localization and insertion processes, there may be variations in setting, subject, and/or provider characteristics. While early VerTouch testing has not evidenced any corresponding variations in device usability and/or outcomes associated with these variations, the study is designed to capture them.

Accordingly, EM, neurology, and anesthesiology settings will be approximately evenly represented in the study, with at least 24 subjects enrolled in each. To adequately represent patients undergoing obstetric and orthopedic procedures, enrolled anesthesiology subjects will be approximately evenly split between these sub-settings. The PM setting will not be included in the study, as there are limitations, particularly with respect to reimbursement, for ESIs performed with palpation or other non-fluoroscopic techniques. However, PM providers will be represented in IntuiTap's summative usability study, and undergo the same

anesthesiology training as those clinical study investigators specialized in obstetrics and orthopedics.

Additionally, investigators will form a representative sample of typical neuraxial procedure providers, including MDs (residents, fellows, and attendings), PAs, and CRNAs, where applicable. Residents must be in their second post-graduate year and above, having performed at least 5 neuraxial procedures in the past 12 months, and are considered trainees. Apart from their level of training, investigators should have a representative range of relevant experience, indicated by the approximate number of neuraxial procedures they have performed in the past year. To ensure adequate user variability, a single investigator should perform no more than 20% of procedures in his/her setting (corresponding to a minimum of approximately 6 procedures per investigator). Any provider type not included in the study will have been assessed in formative and/or summative human factors testing.

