7.4 Clinical Procedures

7.4.1 Visit 1

Screening

At the screening visit the following activities and information will be collected:

- Informed Consent
- Physical Examination (height/weight)
- Eligibility Determination
- Randomization and Subject ID Assignment

- Demographics (gender, age, race, ethnicity)
- Relevant Medical History
- Concomitant Medications

At Treatment

At the time of treatment, the following activities and information will be collected:

- Concomitant Medications
- Pain and/or anti-anxiety medication(s) given for the procedure
- Provider level of training (e.g. resident, fellow, attending, PA, CRNA, NP)
- Provider number of years of in practice
- Provider experience (i.e. number of neuraxial procedures performed in the past 12 months)
- Provider specialty (i.e. emergency medicine, neurology, anesthesiology)
- Procedure setting (i.e. emergency medicine, neurology, orthopedic anesthesiology, obstetric anesthesiology)
- Type of neuraxial procedure (i.e. diagnostic LP, therapeutic LP, spinal anesthesia, epidural anesthesia, CSE, blood patch)
- Reason for Neuraxial Procedure (if not diagnostic LP or blood patch), such as:
 - Therapeutic LP: CSF drainage, intrathecal injection, other
 - Orthopedic procedure: total hip replacement, total knee replacement, other
 - Obstetric procedure: labor/induction, cesarean section, hysterectomy, tubal ligation, other

The subject will be treated with the device or control, per **Figure 6** below (see IFU for more detailed VerTouch steps)^[24]. Initial landmarking for vertebral level is performed by standard technique in both groups in order to identify a safe level when placing the drape to expose the procedure area.

Listed data will be recorded in source documentation, by a member of the study team designated as an observer, as they become available. The observer will also be responsible for counting needle insertions and redirections. Note that procedure success may be reported at different points within the treatment, depending on when spinal access can be confirmed for the particular neuraxial procedure.

[figure not shown]

Figure 6. Flowchart of Visit 1 treatment.

Post-Treatment

After the completion of the procedure, the following activities and information will be collected:

- Patient position (seated, lateral decubitus)

- Length, gauge, bevel (cutting, non-cutting), and type (straight, curved) of needle used

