As with the standard of care and the ultrasound alternative, IntuiTap has assessed the potential for risks in the above categories to be exacerbated by certain provider and/or patient characteristics. VerTouch formative and early IRB-approved testing, which has included residents (after their internship) through attendings, and non-MDs, has evidenced no significant difference in use errors and/or insertion performance associated with indicators of provider skill, such as provider level of training or experience with neuraxial procedures. However, to protect the direct risk to subjects, all Investigators will receive the same training on the use of the device and on study procedures, and must be approved by IntuiTap prior to enrollment. Training will follow a checklist that aligns with the IFU, and will include hands-on interaction with the Device. With regard to patient characteristics, formative testing has evidenced some challenges associated with using the Device in simulated patients with high BMI and/or in the lateral-decubitus position, but none that significantly impacted insertion performance. To mitigate these, the indications and instructions for use have been refined to ensure safe and effective Device use across indicated patients; and training will include simulated use in representative challenging cases.

IntuiTap has also assessed and mitigated potential risks associated with the Device being left in place during needle insertion. For example, with an earlier version of the Device, there was a potential concern that while the

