EM, neurology, and anesthesiology settings will be approximately evenly represented in the study, with at least 24 subjects enrolled in each. To adequately represent patients undergoing obstetric and orthopedic procedures, enrolled anesthesiology subjects will be approximately evenly split between these sub-settings. The PM setting will not be included in the study, as there are limitations, particularly with respect to reimbursement, for ESIs performed with palpation or other non-fluoroscopic techniques. However, PM providers will be represented in IntuiTap's summative usability study and undergo the same anesthesiology training as those clinical study investigators specialized in obstetrics and orthopedics.

Investigators will form a representative sample of typical neuraxial procedure providers, including MDs (residents, fellows, and attendings), PAs, and CRNAs, where applicable. Residents must be in their second post-graduate year and above, having performed at least 5 neuraxial procedures in the past 12 months, and are considered trainees. Apart from their level of training, investigators should have a representative range of relevant experience, indicated by the approximate number of neuraxial procedures they have performed in the past year. To ensure adequate user variability, a single investigator should perform no more than 20% of procedures in his/her setting. Any provider type not included in the study will have been assessed in formative and/or summative human factors testing.

Client/Project	IntuiTap/VerTouch
Version and Date	V02 – 22 December 2020

5 Sample Size Justification

It is expected that approximately 120 subjects will be screened to meet a target enrollment goal of 96 subjects (48 in each group) across 3 investigational sites. The superiority hypothesis for the number of insertion attempts with IntuiTap (μ_1) and palpation (μ_2) is:

$$H_0: \mu_1 \geq \mu_2 \text{ vs } H_1: \mu_1 < \mu_2$$

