At the time of treatment, data will be collected on concomitant medication; pain and/or anti-anxiety medication(s) given for the procedure; provider level of training, number of years in practice, experience, and specialty; procedure setting; and type of and reason for neuraxial procedure. The subject will be treated, either with the device or the control. The designated observer will also be responsible for counting needle insertions and redirections. Post treatment, the subject will be monitored for adverse events, adverse device effects or other reportable observations to ensure safety, entering relevant data into the eCRF.

A follow-up visit will be conducted at 3 ± 2 days following treatment. The presence of PDPH and potential adverse events will be assessed in all subjects. At the conclusion of the follow-up visit, a Subject Study Exit CRF will be completed. Adverse events identified in the study will be followed to resolution.

Assessment	Visit 1	Visit 2
------------	---------	---------

Statistical Analysis Plan

Client/Project	IntuiTap/VerTouch
Version and Date	V02 – 22 December 2020

	Screening	Treatment	Post-Treatment	Follow-up
Demographics	X			
Medical History	X			
Physical Exam (Height & Weight)	X			
Inclusion/Exclusion Criteria	X			
Informed Consent	X			
Randomization	X			
Concomitant Medications	X		X	
Procedure Completion		X		
Discomfort Assessment			X	
Provider Satisfaction Assessment			X	
PDPH				X
Adverse Event Assessment			X	X
Adverse Device Effect Assessment			X	X

7 Study Populations

The study populations are defined as follows:

- Intent-to-treat population (ITT): All randomized subjects according to their randomized group.
- Per-protocol population (PP): All subjects who received their randomized treatment, did not have an inclusion or exclusion criteria violation, had a procedure success, and did not have a major protocol deviation.

The primary analysis and all study results will be analyzed using the ITT population. The primary analysis will be repeated using the PP population. Subjects who meet the discontinuation criteria will be discontinued from the study.

8 Statistical Methods

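### Nothing in the text shown fixes the operator before the arm is known; naming the operator first and then releasing a concealed assignment at treatment is a cheap improvement

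*Protocol*

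**What the plan says.** **Allocation.** Protocol 6.1: "subjects will be randomized 1:1 into two groups via the block randomization method with a list held in each test setting". SAP 4 repeats this, and Protocol 7.3 adds that blocking is within setting. Neither document gives the block size, who holds the list, or how an assignment is revealed.

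**When the arm is assigned.** Protocol 7.4.1 lists "Randomization and Subject ID Assignment" under Screening. Table 2 of the Protocol and the schedule in SAP 6 both mark randomization in the Screening column. Protocol 6.4.3 has the scheduled procedure date recorded at screening.

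**When the operator appears.** The At Treatment list in Protocol 7.4.1 includes "Provider level of training (e.g. resident, fellow, attending, PA, CRNA, NP", with years in practice, experience and specialty. SAP 6 agrees: "At the time of treatment, data will be collected on concomitant medication; pain and/or anti-anxiety medication(s) given for the procedure; provider level of training".

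**Who may operate.** Protocol 6.1 admits residents from the second post-graduate year, fellows, attendings, PAs and CRNAs. The limit on each is that "a single investigator should perform no more than 20% of procedures in his/her setting (corresponding to a minimum of approximately 6 procedures per investigator"). SAP 4 keeps the cap without the bracket: "a single investigator should perform no more than 20% of procedures in his/her setting".

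**Analysis.** The primary test (Protocol 8.2.2, SAP 8.3.3.2) is a bootstrap of the difference in mean attempts, resampling cases within arm, one-sided 0.025, with no operator term. Provider type, MD level, years and experience enter only exploratory models, one at a time, on log attempts (SAP 8.3.3.4).

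**The concern.** The endpoint is a count produced by the person holding the needle, so who operates is part of what is being compared. Randomization balances patients at the moment of assignment. It balances operators only if the operator is already settled then, or is settled later without regard to the arm. The text requires neither.

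If more experienced staff tended to take one arm, the difference in means would mix the device effect with an operator effect. The bootstrap would treat that mixture as the device effect. Analysis by randomized group keeps patients in their arms but does nothing for operator balance. The exploratory models could reveal an imbalance after the fact. They use provider categories rather than individual operators, work on another scale, and would not change the primary result. The distortion could favor the device or hide a real benefit.

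**Working it through.** **Inputs from the documents.** 48 per arm, about 32 per setting if the 96 are spread evenly over three settings; palpation mean 2.1 and SD 1.5, with a literature SD of 2.8; VerTouch mean 1.1 and SD 0.6; one-sided 0.025.

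**Assumed inputs, not in the documents.** A gap in mean attempts between less and more experienced operators of 0.3 or 0.5, the same under both methods; half of all procedures done by the more experienced group; a split of that group by arm of 60% v 40% or 70% v 30%.

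**1. The plan's own figures.**
- Power for first-attempt success, 50% v 81% at 48 per group: (0.31 - 1.96 x sqrt(2 x 0.655 x 0.345/48)) / sqrt((0.25 + 0.1539)/48) = 1.306, and Phi(1.306) = 0.904. The stated 90% reproduces.
- Cap: 0.20 x 32 = 6.4, so 6 whole procedures, matching the Protocol's approximate 6.

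**2. What the cap permits.** With 16 cases per arm in a setting, three operators could do 6 + 5 + 5 = 16 VerTouch cases and three others the 16 palpation cases. No one exceeds 6. The cap therefore does not constrain operator balance between arms. This shows what is allowed, not what is expected.

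**3. Operator-made difference with no device effect.** Difference = gap x (experienced share in one arm - experienced share in the other).
- Gap 0.3: 0.3 x 0.20 = 0.06; 0.3 x 0.40 = 0.12.
- Gap 0.5: 0.5 x 0.20 = 0.10; 0.5 x 0.40 = 0.20.

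**4. One-sided error.** SE = 1.5 x sqrt(2/48) = 0.306. Error = P(Z > 1.96 - difference/SE).

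| False difference | Error, SD 1.5 | Error, SD 2.8 | Simulated bootstrap, SD 1.5 |
|---|---|---|---|
| 0 | 2.5% | 2.5% | 2.6% |
| 0.06 | 3.9% | 3.2% | 4.1% |
| 0.10 | 5.1% | 3.7% | 5.6% |
| 0.12 | 5.8% | 4.0% | 6.4% |
| 0.20 | 9.6% | 5.4% | 10.4% |

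The simulation used a percentile bootstrap (the documents name no type) on a count distribution fitted to mean 2.1, SD 1.5 and 50% first-attempt success. A separate simulation with geometric counts and a 0.5 gap gave 5.8% at 62.5 v 37.5 and 11.2% at 75 v 25. With operators unrelated to arm it gave 2.3% to 3.0%.

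**5. Sorting the other way.** With the planned true difference of 2.1 - 1.1 = 1.0 and SE = sqrt((1.5^2 + 0.6^2)/48) = 0.233, normal-approximation power is 99%. Shrinking the difference by 0.1 or 0.2 gives 0.9/0.233 - 1.96 = 1.90 (97%) or 0.8/0.233 - 1.96 = 1.47 (93%).

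**6. If the operator is fixed first.** Only chance imbalance remains. The difference in experienced share has SD sqrt(2 x 0.25/48) = 0.102, about 10 percentage points, and the test's nominal error already allows for it.

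**The case against.** **Collection is not choice.** The schedules say when operator details are written down, not when the operator is decided. A provider settled days earlier could still be recorded at treatment. Screening and treatment share Visit 1, and Protocol 6.4.2, which speaks of recruiting subjects from investigators, hints at an earlier link. Figure 6 is the Visit 1 flowchart and is not shown, so an operator step drawn there cannot be excluded. All of this stands. It limits the point to the absence of a requirement in the text available.

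**The sponsor's evidence on skill.** Protocol 9.2.1 reports that early testing "has evidenced no significant difference in use errors and/or insertion performance associated with indicators of provider skill", and that "all Investigators will receive the same training on the use of the device and on study procedures". The first statement concerns VerTouch, comes without figures and does not cover palpation, which is half of the contrast. The second means there is no training reason to sort operators, and that counts against expecting it. It does not settle who operates.

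**Detectability.** Operator factors are captured and summarized by arm, so gross sorting would be visible. True, but visibility does not restore the primary test.

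**Stronger readings the documents do not support.** A reader might infer that sites will assign operators by arm; nothing says so. A reader might infer that the list is open to staff because it is kept in the setting; it could already be in sealed envelopes, and leaving the block size out of a site document is itself compatible with concealment. A reader might infer a severe error rate by assuming an operator gap as large as the whole planned effect of 1.0; no figure in the documents supports such a gap.

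**Conclusion.** The point holds as a design improvement, not as a demonstrated bias. In the text shown, the arm is assigned at Screening, nothing ties the operator down beforehand, the cap ignores arm, and the primary analysis cannot absorb an operator imbalance.

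On size, a false difference of 0.1 to 0.2 attempts would lift the one-sided error from about 2.5% to about 5-6% and 10%. That rests on SD 1.5, an assumed 0.5-attempt gap present in both arms, and assumed splits of 60 v 40 and 70 v 30. A smaller gap or a larger SD gives less. Sorting against the device would cost a few points of power on the planned assumptions. Confidence that the requirement is missing from the text is good; confidence that it matters in practice is moderate, because the gap and the degree of sorting are unknown. The change is recommended because it is cheap before enrollment and the imbalance cannot be reliably undone afterwards.

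**What to change.** **Sequence (Protocol 7.4.1, Table 2; SAP 6).** Record the named operator first, then release the assignment at treatment, as close to the procedure as practical. Move the randomization mark from Screening to Treatment and add a row for naming the operator before randomization. Record any later change of operator, including a takeover during the procedure. The existing rules on randomized groups and total insertions already cover how such a subject is counted.

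**Concealment (Protocol 6.1 and 7.3; SAP 4).** Replace the list held in each setting with a stated concealed release: sequentially numbered opaque sealed envelopes, or release through the eCRF. Use randomly varying block sizes that are not disclosed to sites, and keep stratification by setting.

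**Cost.** A few sentences in each document and one row in each schedule table. Envelopes need no new system; eCRF release would need a module the documents do not describe. Sites take on a short extra step before the procedure, must have a device kit at hand before the arm is known, and lose some freedom to swap operators. Sample size, endpoint and primary test are unchanged.

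Separately, and only as an editorial matter, Protocol 6.1 describes the cap's six procedures as a minimum although a cap sets a maximum; the two should be reconciled.
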